2. OBJECTIVES

2.1. PRIMARY ENDPOINT

To evaluate the safety of idelalisib, as post alloHSCT maintenance therapy in patients with B-cell hematologic malignancies, by comparing to placebo.

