6. STUDY STATISTICS

This is a phase I study of Idelalisib, an orally-administered, selective inhibitor of Phosphoinositide 3 kinase (PI3K)- δ . It has been successfully used pre-transplant to induce partial and complete responses in many B-cell derived malignancies. In this study Idelalisib will be evaluated in the post-transplant setting. Patients receiving a standard of care allogeneic hematopoietic stem cell transplant from any source: cord, marrow, or peripheral blood will be eligible. Patients will be randomized in a 2:1 ratio to either 100 mg Idelalisib twice daily from day 90 (\pm 10 days) following transplant, Arm A, or a placebo, Arm B, and monitored for toxicity until day 270.

Study treatment plan: Idelalisib day +90 [+/- 10 days), 100mg twice daily, and at least 5 days after the discontinuation of filgrastim if ANC is greater than 1,000 and PLT 50>Gi/L and <grade 2 aGVHD. Patient's Idelalisib will be dose adjusted for the expected toxicities of Idelalisib including pneumonitis, hepatitis, neutropenia, thrombocytopenia and loose stools.

Primary endpoint and design: The primary goal of this study is to evaluate the safety of Idelalisib as post-transplantation maintenance in patients undergoing an allogeneic BMT. In addition to the allowed dose reductions, a safety monitoring plan will be implemented to ensure that other treatment-limiting events are not elevated. The study will be monitored between the date of randomization and day 270 post-transplant. For safety monitoring, treatment-limiting toxicities will be defined as Idelalisib interruption for >14 days, or other grade 3 or higher adverse events as defined by CTCAE IV not captured in the protocol for dose de-escalation. The trial will assume that, *a priori*, the probability of these events in both arms of the study will follow a Beta (0.10, 0.90) prior distribution. This distribution corresponds to an assumption that 10% of patients might experience a treatment-limiting toxicity.

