Sample size/accrual Rate: The accrual rate for this study is expected to be 20 patients per year. The total sample size will be 45 patients, 30 on the Idelalisib arm (Arm A) and 15 on the control arm (Arm B). The safety objective of this trial is based on the precision of estimating the specified treatment-limiting toxicity events. An approximation to the precision will be made using binomial confidence intervals. Thirty patients on the Idelalisib arm will allow us to estimate the proportion of patients experiencing post-transplant events with a precision of $\pm 0.19\%$.

Interim analyses and operating characteristics: For monitoring we will compute the posterior probability of a treatment-limiting toxicity between day 90 and 270 in each arm of the study, given the data and prior distribution, Beta(0.10, 0.90), and evaluate whether to hold accrual after fixed cohorts of patients. Monitoring will occur in groups of 15 patients, beginning after the first 10 enrolled on Arm A. The maximum sample size will be 45 patients, 30 in Arm A and 15 in Arm B. The stopping rule will recommend a safety review if it becomes clear that the posterior probability of a treatment-limiting toxicity in Arm A exceeding Arm B by 0.10 is 75% or greater. Operating characteristics of the study with Arm B treatment-limiting toxicity of either 5%, Table 1, or 10%, Table 2, and varying toxicities in Arm A are based on 1,000 simulations of the trial.

Table 1. Scenarios with control arm (Arm B) treatment-limiting toxicity of 5%
Both arms prior: Beta (0.10, 0.90), assumes prior for toxicity is 10%, delta of 0.10, and 75% cutoff.
2:1 randomization Total N=45

	Delta=0.10	Delta=0.10
Scenario: Control, Idelalisib	Stopped for toxicity	Avg. sample size Control, Idelalisib
1: 0.05, 0.05	1.3%	14.9, 29.8
2: 0.05, 0.10	6.8%	14.4, 28.8
3: 0.05, 0.15	19.2%	13.4, 26.8
4: 0.05, 0.20	32.4%	12.3, 24.7
5: 0.05, 0.25	53.1%	10.5, 21.0
6: 0.05, 0.30	68.2%	9.3, 18.7
7: 0.05, 0.35	82.3%	8.0, 16.0
8: 0.05, 0.40	89.8%	7.1, 14.2
9: 0.05, 0.45	94.9%	6.3, 12.6

Table 2.

Scenarios with control arm (Arm B) treatment-limiting toxicity of 10%

Both arms prior: Beta(0.10, 0.90), assumes prior for toxicity is 10%, delta of 0.10 and 75% cutoff.

2:1 randomization Total N=45

	Delta=0.10	Delta=0.10
Scenario: Control, Idelalisib	Stopped for toxicity	Avg. sample size Control, Idelalisib
1: 0.10, 0.10	4.9%	14.6, 29.1
2: 0.10, 0.15	12.0%	13.9, 27.8
3: 0.10, 0.20	27.9%	12.7, 25.4
4: 0.10, 0.25	44.3%	11.4, 22.8

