5: 0.10, 0.30	59.0%	10.1, 20.2
6: 0.10, 0.35	70.7%	9.3, 18.5
7: 0.10, 0.40	83.4%	8.1, 16.1
8: 0.10, 0.45	90.0%	7.3, 14.5
9: 0.10, 0.50	94.4%	6.6, 13.1

Secondary endpoint:

1. Event-free survival at one year.

Analysis Plans:

Toxicities will be summarized descriptively by grade and type. Cumulative incidences of aGVHD, relapse, and NRM will also be computed using Fine and Gray's method for competing risks. Treatment of relapse/progression, graft failure, and death are considered competing risks for GVHD; relapse/progression is a competing risk for NRM; and death before relapse/progression is a competing risk for relapse/progression. In addition, we plan to report aGVHD incidences with only graft failure and death regarded as competing risks.

Using the Kaplan-Meier method, the probability of 1-year event-free survival will be estimated and reported with 95% confidence intervals. The proportions of patients who are event-free at 1 year will also be estimated with a 95% exact binomial confidence interval.

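### The primary objective is a safety comparison with placebo, but no final between-arm estimate of treatment-limiting toxicity is prespecified

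*Combined protocol and SAP*

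**What the plan says.** Section 2.1 (Primary endpoint) frames the objective as the safety of idelalisib as "maintenance therapy in patients with B-cell hematologic malignancies, by comparing to placebo". Section 6 restates it without mentioning placebo: "The primary goal of this study is to evaluate the safety of Idelalisib as post-transplantation maintenance in patients undergoing an allogeneic BMT". Section 6 also sets 2:1 allocation, with 30 patients on idelalisib (Arm A) and 15 on placebo (Arm B).

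On sizing, section 6 says: "The safety objective of this trial is based on the precision of estimating the specified treatment-limiting toxicity events". The precision it then gives is for one arm: "Thirty patients on the Idelalisib arm will allow us to estimate the proportion of patients experiencing post-transplant events", to within 0.19 (printed with a percent sign). No precision is given for Arm B or for the difference.

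The arms are compared in the interim monitoring paragraph. Each arm's treatment-limiting toxicity (TLT) rate has a Beta(0.10, 0.90) prior, and a safety review is recommended if the posterior probability that Arm A exceeds Arm B by 0.10 is at least 75%. Tables 1 and 2 give simulated operating characteristics for 18 two-arm scenarios. Sections 5.1 and 8.2 refer to a differential above 10%, again as a stopping rule.

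On final analysis, the Analysis Plans say of toxicity only: "Toxicities will be summarized descriptively by grade and type". They name no TLT endpoint, split by arm, difference or interval. The secondary endpoint, one-year event-free survival, does get 95% intervals.

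**The concern.** Fifteen patients are randomised to placebo so that toxicity on idelalisib can be set against background toxicity after transplant. The estimate that would answer that question is the difference in TLT proportions, and the plan never says it will be calculated or reported. The monitoring rule uses the right contrast, but its output is a yes/no prompt during accrual. At the end the investigators would hold descriptive tables and the knowledge that the rule did or did not fire. Neither tells a reader how large an excess the data support or exclude, which is what the later large randomised trial mentioned in the introduction would need. An analysis chosen after unblinding could also be questioned as selective.

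**Working it through.** **Inputs.** From section 6: 30 v 15 patients, Beta(0.10, 0.90) prior in both arms, margin 0.10, cutoff 75%, monitoring in groups of 15 starting when Arm A has 10, and control rates of 5% and 10%. The confidence level behind the precision figure is not stated; I assume 95%.

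**1. The plan's own figure.** The widest exact (Clopper-Pearson) 95% interval at n = 30 is for 15/30: 0.313 to 0.687, half-width (0.687 − 0.313)/2 = 0.187, which rounds to 0.19. The Wald maximum is 1.96 × √(0.25/30) = 0.179. The printed figure reproduces as a proportion, for Arm A only.

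**2. The same figure for the difference.** Wald half-width = 1.96 × √[pA(1 − pA)/30 + pB(1 − pB)/15]:

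| Placebo v idelalisib | Difference | Arm A alone |
|---|---|---|
| 5% v 5% | 0.14 | 0.08 |
| 5% v 15% | 0.17 | 0.13 |
| 5% v 20% | 0.18 | 0.14 |
| 10% v 10% | 0.19 | 0.11 |
| 10% v 20% | 0.21 | 0.14 |
| 50% v 50% | 0.31 | 0.18 |

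For example, at 10% v 20%: 1.96 × √(0.16/30 + 0.09/15) = 1.96 × √0.01133 = 0.21. Wald is rough here: 5% of 15 patients is 0.75 expected events.

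**3. How often the rule stays silent at a true 15-point excess (5% v 20%).**
- Protocol Table 1, scenario 4: stopped in 32.4%, so silent in 100 − 32.4 = 67.6%.
- Exact enumeration of the stated rule with looks at 10/5 and 20/10 (Arm A/Arm B): fires in 46.2%, silent in 54%.
- With a third look at 30/15: fires in 58.6%, silent in 41%.

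The text does not say whether a look at 45 patients, when accrual is complete, counts. The mismatch with Table 1 is a separate matter; the conclusion does not depend on which figure is right.

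**4. Final results that leave the rule silent at 30 v 15.** Posteriors are independent: Beta(0.10 + x, 0.90 + n − x) in each arm.

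| Arm A v Arm B | P(pA − pB > 0.10) | Median | 95% credible interval |
|---|---|---|---|
| 4/30 v 0/15 | 0.63 | +0.12 | about +0.03 to +0.27 |
| 6/30 v 1/15 | 0.64 | +0.13 | −0.07 to +0.31 |
| 8/30 v 2/15 | 0.62 | +0.13 | −0.11 to +0.34 |

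All three fall below 0.75. In the first, the trial's own model puts the whole interval above zero (lower limit 0.025 before rounding), yet nothing in the plan would report it. That lower limit depends on the prior, which puts much of its weight near zero when Arm B has no events. The Newcombe 95% interval for the same data uses Wilson limits 0.053 to 0.297 for 4/30 and 0 to 0.204 for 0/15. Its lower limit is 0.133 − √(0.080² + 0.204²) = −0.09 and its upper limit is 0.133 + (0.297 − 0.133) = 0.30. The choice of interval can therefore change the reading, which is a reason to fix it in advance.

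**The case against.** The strongest reply is that the design does compare the arms. The between-arm posterior is defined, and the 30:15 allocation was simulated on it in 18 scenarios. That stands: a reader might infer that the whole design was sized on Arm A alone, but this is true only of the precision sentence. The reply does not supply a final estimate, because the posterior is introduced for monitoring and no reporting of it is planned.

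Second, descriptive toxicity reporting is usual in a 45-patient phase I trial, and section 6 restates the goal without placebo. That argues against a formal test, and I do not ask for one: approximate power for a 10-point excess at two-sided 5% is only 13% (5% v 15%) and 11% (10% v 20%). It does not argue against an estimate when section 2.1 names the comparison and patients are randomised to it.

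Third, nothing forbids showing results by arm, and the reference to binomial confidence intervals implies at least an interval for Arm A. That also stands. A reader might infer that the plan would call the drug safe whenever the rule does not fire, or that no interval at all would appear. The documents say neither. What is missing is prespecification of the difference.

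Finally, it is tempting to say the comparison is 1.7 times less precise than the plan claims. Against the quoted 0.19, the worst case is 0.31/0.19 = 1.63, and it needs 50% toxicity in both arms. At the planning rates the half-width of the difference is close to 0.19. The factor √3 = 1.73 applies only like for like, against Arm A at the same common rate.

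**Conclusion.** The point holds in this form: section 2.1 sets a placebo comparison as the primary objective, and no final between-arm estimate of TLT is prespecified. The stated precision is for Arm A only, and the between-arm posterior serves only as a trigger. Silence from that trigger is weak reassurance: a true excess of 15 points (5% v 20%) passes unflagged in 41% to 67.6% of trials, depending on the number of looks and on whether Table 1 or the exact calculation is used. The expected 95% half-width of the difference is about 0.14 to 0.21 at the planning rates and at most 0.31, against 0.08 to 0.14 and at most 0.18 to 0.19 for Arm A alone. These figures assume a 95% level, Wald intervals (exact for the 0.19), full accrual of 30 and 15, and the stated priors. This is a gap in the analysis plan that should be closed; it does not make the design invalid.

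**What to change.** In the Analysis Plans, add as the primary analysis: the number and proportion of patients with TLT through day 270 in each arm; the difference pA − pB with its 95% credible interval; and P(pA − pB > 0.10), all from the Beta(0.10, 0.90) model already specified for monitoring. A named 95% confidence interval for the difference would also do, provided the method is stated. If the Bayesian interval is chosen, give the confidence interval as a sensitivity analysis, since the prior matters when Arm B has few or no events.

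In the sample-size paragraph, state the expected half-width of the difference beside the Arm A figure, with its confidence level: about 0.14 to 0.21 at the planning rates and at most 0.31.

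The cost is a few lines of text. Sample size, data collection and the monitoring rule do not change. The downside is that the stated precision becomes less favourable, and readers will see that 45 patients leave a wide interval for the excess.

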7. CORRELATIVE STUDIES

7.1 RATIONALE AND OUTLINE OF CORRELATIVE STUDIES

The overarching goals of our correlative studies are to:

- i) Characterize the effect of Idelalisib on allogeneic T and B cells, particularly on their re-distribution, in vivo expansion, activation, and effector differentiation after treatment
- ii) Identify potential predictive biomarker candidates to allow for better selection of patients after alloBMT who may benefit or whom are likely to have toxicity from Idelalisib therapy.
- iii) Characterize the mechanisms of relapse after Idelalisib such as B cell and T cell dysfunction.

Hypothesis: We hypothesize that Idelalisib administration will have an effect on GVHD modulation. This prediction is based on the data suggesting that PI3K pathway is activated in activated/memory T cells responsible for autoimmunity (16). Interestingly, Ali et al., have recently shown that PI3K α inactivation results in the disruption of two tumor-associated immune-suppressive cell types- regulatory T cells and myeloid-derived suppressor cells (17). Thus, we also hypothesize that p110 α inhibition with Idelalisib can enhance allogeneic antitumor immunity post-transplant that can be measured as increased TCR diversity and the emergence of unique TCR clonotypes.

Flow Cytometry Studies: We will perform multi-color flow cytometry on peripheral blood (PB) and bone marrow (BM) specimens before and after Idelalisib treatment using three pre-determined panels of mAbs including but not limited to those specific for CD3, CD4, CD8, PD-1, CD45RA, CCR7, CD25, CD27, CD28, CD69, Ki-67, T-bet, CD127, FoxP3, HLA-DR, CTLA-4, TNFR11, TIM3, LAG-3, CD160, 2B4, BTLA, KLRG-1, CD16, and CD56. This multi-color approach allows examination of different CD4+ and CD8+ T cell subpopulations (expressing CD45RA, CCR7, CD27, and CD28), phenotypic separation of human CD4+FoxP3+ T cells into three distinct subpopulations as well as assessment of their proliferative status (% Ki-67 positive cells). (18) The expression of CD69, HLA-DR and TNFR11 will be measured to characterize T cells activation status and the expression of co-inhibitory molecules (PD-1, TIM3, LAG-3, CD160, 2B4, BTLA, KLRG-1) will be studied. Natural killer cells (NK), NK-T cells will be enumerated using CD16 and CD56 (NK/NK-T cells). Additionally effects of Idelalisib on myeloid-derived suppressor cells and B cell depletion post-transplant will be assessed. As a part of PBMCs collection and mononuclear cell isolation we will also collect plasma that will be stored and used for measurement of defined cytokines (IL-2, IL-6, IL-10, IFN- γ , TNF- α) to assess Idelalisib -induced global T cell activation or for proteomic analysis of defined molecules associated with GVHD (proteomic studies on PTCy-based platforms are being prepared for publication (20)).

Molecular studies: Immune Profiling of T cell Repertoire: The studies proposed will evaluate the T cell receptor (TCR) diversity in T cells isolated from PB and BM from patients before and after treatment with Idelalisib on the parent clinical trial. We will determine TCR diversity and clonal composition using a molecular

and computational approach based on high-throughput DNA sequencing of rearranged TCR β CDR3 regions from T cell genomic DNA. This approach allows direct measurement of the TCR β CDR3 region sequence diversity in any arbitrarily complex population of T cells, and also permits quantitative description of the clonal composition of the population. (19) The [name] laboratory in collaboration with the [name] laboratory from Fred Hutchinson Cancer Research Center (FHCRC) have performed extensive monitoring and tracking of the TCR repertoires in patients undergoing alloHSCT (manuscript in preparation). We are utilizing an established multiplex PCR strategy to amplify the CDR3 region of the TCR, spanning the variable region formed by the junction of the V, D and J segments and their associated non-template insertions followed by Illumina-based sequencing methodology, an well-characterized methodology developed by Adaptive Technology (<http://www.adaptivebiotech.com/technology/>). Sequencing is followed by comprehensive bioinformatics analyses focused on determining the diversity of the T cell and B cell repertoires as well as the entropy and clonality of each repertoire consistent with previous studies. Through these ongoing studies we have developed substantial experience not only in using and analyzing DNA retrieved from unsorted PBMCs but also from sorted T cells subpopulations (naïve vs memory vs regulatory), paired PB and BM samples and as well from DNA retrieved from FFPE archived tissues.

The long-term goal of this correlative work is to uncover biomarkers that in future may predict better integration of Idelalisib post-transplant. This correlative work will also provide deeper insight into the, effects of Idelalisib on GVHD and allogeneic anti-tumor immunity as well as on the mechanisms of failure to eradicate B cell malignancies after Idelalisib treatment.

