7.2 Analysis of Correlative Endpoints

The analyses of pre- and post-treatment PB and BM specimens for immune parameters will be descriptive and graphical in nature. Data will be summarized for each cohort separately. The change in flow values at each time point after Idelalisib relative to the baseline value will be checked for skewness and log-transformed as appropriate. The changes will be modeled using mixed-effects, linear regression models that included fixed effects for time and a random effect for the patient to account for within-patient correlation of measurements. To explore potential differences in the change in flow values across patient subgroups, interaction terms will be included in the regression models. Post-treatment changes in gene expression in immune gene signaling circuits in tumor biopsies and PB will be summarized with descriptive statistics and correlated with clinical outcomes.

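### The T-cell receptor measures of antitumor immunity, read before versus after idelalisib, cannot separate a drug effect from sampling or post-transplant recovery, and the plan does not use the placebo arm, which could

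*Combined protocol and SAP*

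**What the plan says.** Section 7.1 states a directional hypothesis and how it would be seen: idelalisib "can enhance allogeneic antitumor immunity post-transplant that can be measured as increased TCR diversity and the emergence of unique TCR clonotypes". The molecular studies paragraph of 7.1 describes the TCR material as coming "from patients before and after treatment with Idelalisib on the parent clinical trial"; placebo patients are not mentioned there. The bioinformatics is to cover diversity "as well as the entropy and clonality of each repertoire consistent with previous studies". No index is chosen, no common depth is set, and neither unique nor emergence is defined.

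Section 7.2 says the analysis of immune parameters "will be descriptive and graphical in nature" and adds: "Data will be summarized for each cohort separately". Its mixed-effects models are for flow cytometry values only. The one fixed effect named is time; the interaction terms are for unspecified patient subgroups. There is no arm term and no TCR-specific analysis.

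On the other side, section 6 randomizes 2:1 to 30 idelalisib and 15 placebo patients, and the schedule in section 4.3 takes correlative samples without restricting them to one arm. Section 2.3 makes the biomarker work a tertiary, exploratory endpoint.

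**The concern.** A blood sample captures a small part of a patient's T-cell repertoire, so two samples from an unchanged repertoire will differ. Many clonotypes in the second sample are new only because the first sample missed them. A measure that counts such clonotypes as emerging responds to sampling whether or not the drug does anything. Observed diversity also depends on how many T cells are sequenced, and these patients are sampled from about day +90 after transplant, when the repertoire may be changing anyway.

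At stake is the statement on immune mechanism and the choice of biomarkers for later work, which section 7.1 names as its long-term goal. A pre/post change within idelalisib patients could be reported as drug-induced immunity when it reflects sampling, depth or recovery.

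**Working it through.** The plan gives no threshold, sample size or effect size for the TCR measures, so there is no figure to reproduce. The check asks what each part of the measure does when nothing changes.

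**Inputs from the documents.** The two-part measure and pre/post contrast (7.1); about 40 mL blood per time point, with no T-cell number, DNA mass or template count fixed (7.3); 30 and 15 patients (section 6).

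**Assumptions.** 10,000, 100,000 or 1,000,000 clonotypes; power-law frequencies with exponent 0.5, 0.8, 1.0 or 1.2; 1,000, 10,000 or 100,000 templates in each sample, plus a pair with 10,000 then 20,000. Two independent samples were drawn from the same unchanged repertoire, with 20 to 60 pairs per setting.

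**Step 1: clonotype part.** With frequency p_i and depths n1 and n2, the expected new share of second-sample clonotypes is approximately

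sum[(1 − p_i)^n1 × (1 − (1 − p_i)^n2)] / sum[1 − (1 − p_i)^n2].

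Hand check with equal frequencies, 100,000 clonotypes and 10,000 templates: (1 − 1/100,000)^10,000 ≈ e^(−0.1) = 0.905. The mildly uneven repertoire (exponent 0.5) simulates at 0.856.

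Mean new share, selected equal-depth settings:

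| Clonotypes | Exponent | 1,000 templates | 10,000 | 100,000 |
|---|---|---|---|---|
| 10,000 | 0.5 | 85.8% | 40.1% | 0.2% |
| 10,000 | 1.2 | 66.8% | 56.2% | 30.1% |
| 100,000 | 1.0 | 81.7% | 73.5% | 55.8% |
| 1,000,000 | 0.5 | 99.7% | 97.6% | 85.7% |
| 1,000,000 | 1.2 | 74.7% | 72.9% | 69.2% |

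The share depends heavily on the assumptions (0.2% to 99.7%). That at least one new clonotype appears does not: it happened in 100% of pairs in every setting.

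**Step 2: diversity part, equal depth.** Two samples of the same size from the same repertoire are exchangeable, so apart from ties the second is more diverse with probability 1/2. Simulated proportions scattered from 25% to 80% across settings, in line with 50% for 20 to 60 pairs. At 50%, 20 or more of 30 patients rising has probability 0.049, and all 45 rising has probability 0.5^45 = 2.8 × 10^(−14).

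**Step 3: diversity part, unequal depth.** With 10,000 then 20,000 templates, richness rose in 100% of pairs and Shannon entropy in 97% to 100%. Smaller increases also matter: with the second sample 1.5 times deeper, entropy rose in 80% to 100% of pairs; at 1.25 times, in 57% to 100%. Because 7.3 fixes blood volume only, depth could follow the patient's T-cell count. Whether it rises in this trial is not in the documents.

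**Step 4: recovery.** If the true repertoire diversifies after day +90 for reasons unrelated to the drug (an assumption), a pre/post rise appears even at equal depth. Down-sampling cannot remove this; a concurrent control can.

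**Step 5: does the remedy work?** A conditional binomial test of each new clone with Bonferroni correction gave no false emergence in any null setting. For a between-arm comparison of within-patient change (two-sided 0.05, 80% power, both assumed), the detectable difference is (1.960 + 0.842) × sqrt(1/15 + 1/30) = 2.802 × 0.316 = 0.886 SD. Power is 72% at 0.80 SD and 89% at 1.0 SD.

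**The case against.** The sentence in 7.1 is a hypothesis in a rationale section, not a decision rule: it has no threshold and no confirmation step, and the analysis is declared descriptive. Emergence may be meant as expansion, since the first correlative goal mentions in vivo expansion and 7.1 promises a quantitative account of clonal composition. Depth handling may sit in the established methodology that 7.1 refers to. If cohort in 7.2 means arm, placebo summaries will stand beside the idelalisib ones.

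Much of this stands. It rules out the inference, which a reader might draw, that sampling alone meets the whole measure in every patient. The two parts are joined by *and*, and Step 2 shows the diversity part rising in only about half of pairs at equal depth. Near-universal rises need greater depth later, which the plan neither states nor excludes.

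What does not stand is exploratory status as a full answer. A descriptive summary still needs a quantity that can differ between drug and no drug. Side-by-side summaries do not rescue the literal clonotype measure, which is met in essentially every patient in both arms. For diversity they would help, but the text names only the pre/post contrast.

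**Conclusion.** The concern holds in limited form. Taken literally, the emergence of unique clonotypes is uninformative about idelalisib, because sampling alone produces it in essentially every patient. That result held over the whole assumed range; it would weaken only if sequencing captured nearly the entire repertoire. The diversity measure is usable, but as planned it is exposed to unequal depth and to post-transplant recovery.

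A reader might go on to infer that the trial cannot show an idelalisib effect on immunity, or that the hypothesis would be confirmed whatever the drug does. The documents do not support that. The trial is randomized against placebo and the scheduled specimens are not limited to one arm, so a valid comparison is available; the fault is that it is not specified. The endpoint is tertiary, and the safety comparison, the stopping rule and event-free survival are untouched.

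**What to change.** Revise 7.1 and 7.2 as follows.

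1. Down-sample every specimen to a common template count before computing diversity, entropy and clonality, and name the diversity index.
2. Count a clonotype as emergent or expanded only if its change between paired specimens exceeds sampling error on a depth-aware test with false-discovery control. Report this alongside diversity, not in its place, because strong expansion can lower diversity. Step 5 used the stricter Bonferroni correction, so an occasional false call should be expected under false-discovery control.
3. Base any statement about an idelalisib effect on the idelalisib-minus-placebo difference in change from baseline, with a 95% interval, at one scheduled on-treatment visit. Section 4.3 provides Day 1 samples in every other cycle from Cycle 2. Keep Month 12 as a secondary, off-treatment time point: study drug ends at day +270, so if Month 12 counts from transplant it falls about 365 − 270 = 95 days later. State whether baseline is the screening or the Cycle 1 Day 1 sample.

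The cost is analysis-plan wording; no added visits, specimens or patients. The downsides are that down-sampling discards reads from deeper specimens and the measure becomes harder to meet. With complete pairs in all 45 patients the 95% interval is about ±1.96 × 0.316 = ±0.62 SD, and missing pairs will widen it. The result should be reported as an estimate, and a null finding should not be read as absence of effect.
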